### **5.2.1 Randomization**

Participants will be randomized (1:1) to receive either IIV and Tdap simultaneously or sequentially (IIV followed by Tdap) using a permuted block randomization scheme stratified by Lead and Contributing sites. The project statistician at Duke University will generate permuted block randomization schemes which will be uploaded to REDCap. The randomization schedule will not be available to the study staff, so the next randomization allocation will not be known before randomization occurs. Following confirmation of study eligibility criteria during Visit 1, participant randomization will be through REDCap with treatment allocation recorded on the CRF.

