## 7 STATISTICAL CONSIDERATIONS

In collaboration with the CDC and Cincinnati sites, the research team at Duke will oversee the statistical analysis. This pilot study is not designed based on statistical considerations regarding power/sample size in relation to group comparisons. Therefore, descriptive statistics and confidence intervals for continuous variables will be presented (e.g., mean, standard deviation, median, interquartile range, and confidence boundaries). Categorical variables will be summarized with frequencies, percentages, and exact confidence boundaries.

For analysis, data will reside on a secure Duke server maintained by Duke Health Technology Solutions (DHTS). For the study, a database will be developed and a dataset for the study without personal identifiers will be made available to the CDC upon request.

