### 7.1 Analysis Plan

**7.1.1 Study Populations** – There will be two study populations for this study. The Intent-to-Treat (ITT) and Safety populations. The ITT Population includes any participant that was enrolled and randomized into the study. The Safety Population is a subset of the ITT Population excluding those participants that never received the study intervention (either the influenza or Tdap vaccine). Statistical analyses will be performed for both study populations, or the ITT Population only if no participants are excluded for the Safety Population.

**7.1.2 Primary Objective 1** - To assess proportions of reactogenicity events in pregnant women receiving Tdap and IIV simultaneously vs. sequentially

Reactogenicity will be assessed for 7 days following each vaccination visit, as described in Section 5.3. The proportion of women and a 95% exact binomial confidence interval will be presented by treatment group, symptom, and grade level (mild/moderate/severe) for women with injection site reactogenicity within 7 days post-vaccination. This will be presented for each of the four reactogenicity outcomes, using the highest grade reported per woman. A 95% confidence interval of the difference in proportions between the treatment groups will also be presented. Systemic reactogenicity will be presented in a similar fashion. For adverse events, the proportion of women and a 95% exact binomial

confidence interval of adverse events, as well as the total number of adverse events, will be presented by treatment group, severity, and relatedness

**7.1.3 Primary Objective 2** - To assess maternal immune responses and cord blood antibody levels to pertussis antigens, tetanus and diphtheria toxoids, and influenza antigens in the women receiving Tdap and IIV simultaneously vs. sequentially

**7.1.3.1 Pertussis antigens** - Geometric mean titers (GMTs) will be calculated along with 95% confidence intervals for the two treatment groups for each pertussis antigen tested. A 95% confidence interval of the difference in GMTs between the treatment groups will also be presented.

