**7.1.3.2 Tetanus and diphtheria antigens** - The proportion of subjects with seroprotection, defined as  $\geq 0.1$  IU/mL post-vaccination for both tetanus and diphtheria ELISAs, in the two treatment groups will be presented along with 95% exact binomial confidence intervals. Ninety-five percent confidence intervals of these differences in proportions between the treatment groups will also be presented. Given there is no acceptable definition of seroconversion with these assays, we will evaluate the data to derive a potential post hoc definition for seroconversion.

**7.1.3.3 Influenza antigens** - The proportion of subjects with seroprotection (pre- and post-immunization) and seroconversion (4-fold change in endpoint titer relative to pre-immunization baseline or a change from  $<1:10$  to  $\geq 1:40$ ) in the two treatment groups will be presented along with 95% exact binomial confidence intervals. A 95% confidence interval of the difference in proportions between the treatment groups will also be presented. The GMTs for each influenza antigen and 95% confidence boundaries will be presented for both treatment groups. A 95% confidence interval of the ratios in GMTs between the treatment groups will also be presented.

Outcomes listed in Primary Objective 2 may be analyzed using a regression model to adjust for covariates such as BMI or race. This will be performed as a secondary analysis if normality assumptions for model based analyses are met.

**7.1.4 Primary Objective 3** – To assess the feasibility of conducting a larger clinical trial in pregnant women receiving Tdap and IIV simultaneously vs. sequentially

Feasibility will be assessed based on the following benchmarks for recruitment and retention in **Table 6**, as well as adequate and timely collection of data and biospecimens.

Table 6: Proposed Feasibility Benchmarks	
Benchmark	Completion Target
Recruitment and randomization	30-50* subjects during 4 month enrollment period
Retention	98% completion of all in-person and delivery visits
Data collection	$\geq 95\%$ collection of reactogenicity data
Biospecimen collection – maternal	$\geq 95\%$ collection of pre/post-vaccination blood samples

Biospecimen collection – delivery	≥ 95% collection of maternal blood, umbilical cord blood, and placental pathology
-----------------------------------	---

\*enrollment target will depend upon whether additional enrollment occurs at the Cincinnati Site

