**7.1.5 Secondary Objective 1** – To describe maternal and infant outcomes in pregnant women receiving Tdap and IIV simultaneously vs. sequentially

The proportion and 95% exact binomial confidence interval will be presented by treatment group for adverse birth outcomes such as preterm birth, low birthweight and SGA. A 95% confidence interval of the difference in proportions between the treatment groups will also be presented.

**7.1.6 Secondary Objective 2** – To evaluate clinical and histological chorioamnionitis in the women receiving Tdap and IIV simultaneously vs. sequentially

The proportion and 95% exact binomial confidence interval will be presented by treatment group for histological and clinical chorioamnionitis. A 95% confidence interval of the difference in proportions between the treatment groups will also be presented.

**7.1.7 Secondary Objective 3** – To build capacity to study immunogenicity of maternal vaccination in the CISA Project, in collaboration with the CDC lab as described in **Table 7**.

**7.1.8 Exploratory Objective 1** - To assess antibody levels to pertussis antigens at 2 months of life in infants born to women receiving Tdap and IIV simultaneously vs. sequentially

Geometric mean titers (GMTs) will be calculated along with 95% confidence intervals for the two treatment groups for each pertussis antigen tested. A 95% confidence interval of the ratio in GMTs between the treatment groups will also be presented as well as for the infant cord blood versus the 2-month blood draw.

Table 7: Feasibility Benchmarks for CDC lab	
Benchmark	Completion Target
Quality of blood specimens submitted to the CDC lab for serologic response to pertussis antigen	Receipt of ≥95% of blood samples in testable condition
Quantity of blood specimens submitted to the CDC lab for serologic response to pertussis antigen	Receipt of ≥95% of blood samples with sufficient volume for testing
Completion of testing	Completion of testing of ≥95% of testable blood samples.

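### The maternal and cord pertussis contrast has no stated scale, and no maternal or cord GMT comparison commits to using the Day 1 titre or the stratification site

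*Combined protocol and SAP*

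**What the plan says.** **Scale.** Section 7.1.3.1 plans GMTs with 95% intervals by group for each pertussis antigen, and adds: "A 95% confidence interval of the difference in GMTs between the treatment groups will also be presented". It does not say whether the difference is on the log or the titre scale. For influenza, Section 7.1.3.3 says "A 95% confidence interval of the ratios in GMTs between the treatment groups will also be presented". For infants at two months, Section 7.1.8 says "A 95% confidence interval of the ratio in GMTs between the treatment groups will also be presented".

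**Adjustment.** One short paragraph after 7.1.3.3 covers all of Primary Objective 2: "Outcomes listed in Primary Objective 2 may be analyzed using a regression model to adjust for covariates such as BMI or race". It continues: "This will be performed as a secondary analysis if normality assumptions for model based analyses are met".

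**Data available.** Section 5.1 (Visit 1) takes blood from every woman before vaccination. Table 6 in Section 7.1.4 targets at least 95% "collection of pre/post-vaccination blood samples". Section 5.2.1 randomises 1:1 "using a permuted block randomization scheme stratified by Lead and Contributing sites". Baseline enters the Objective 2 analyses only through the influenza seroprotection and seroconversion proportions, never through a GMT comparison.

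**Status of the comparisons.** Section 7 says: "This pilot study is not designed based on statistical considerations regarding power/sample size in relation to group comparisons". Results are therefore estimates with confidence intervals.

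**The concern.** There are two linked gaps in how the immunogenicity contrasts are specified.

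First, a difference between two geometric means on the titre scale depends on the titre level, whereas a ratio does not. Read literally, 7.1.3.1 reports the maternal and cord pertussis result in a different form from the same antigens in infants and from influenza. A lower pertussis response after co-administration is a main reason given for the trial (Sections 1.1 and 1.2), so this contrast should not be open to two readings.

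Second, the strongest candidate predictor of a post-vaccination titre is often the woman's own pre-vaccination titre. It is collected from everyone, yet no GMT comparison commits to using it, or the site that stratified randomisation. Neither is excluded, because the covariate list is open-ended, but nothing is fixed in advance. Whether to adjust, for what, and whether the model runs at all can be decided after the data are seen, in a trial where study staff are unblinded (Section 5.2.2).

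No test or margin is at stake. The intervals are the main group-comparison output, so their form and width are what readers will use.

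**Working it through.** The plan gives no SD, correlation or expected width, so there is no figure of its own to reproduce.

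**Inputs**
- From the documents: 80 women, 1:1, so 40 per arm (Protocol Summary; Section 5.2.1); 60 subjects for influenza testing, so 30 per arm (Section 6.3); two sites and two seasons.
- Assumed: log10 SD 0.4; correlation r between Day 1 and outcome log titre from 0 to 0.7; two equal sites; a 50:50 season split.

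**1. Unadjusted interval for the GMT ratio**

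Half-width on log10 = t(0.975, 2n−2) × SD × √(2/n).
- n = 40: 1.991 × 0.4 × √(2/40) = 0.178, and 10^0.178 = 1.51.
- n = 30: 2.002 × 0.4 × √(2/30) = 0.207, and 10^0.207 = 1.61.

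The interval is the estimated ratio multiplied and divided by that factor.

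**2. Adjusted interval**

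Simulation, 12,000 runs per setting. Model: arm + Day 1 log titre + site + season, with arms balanced within site and no true site or season effect. Change in mean log-scale half-width against the unadjusted interval:

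| r | 40 per arm | 30 per arm |
|---|---|---|
| 0 | +1.4% | +1.9% |
| 0.15 | +0.2% | +0.8% |
| 0.2 | −0.6% | −0.1% |
| 0.3 | −3.3% | −2.8% |
| 0.5 | −12.2% | −11.8% |
| 0.7 | −27.6% | −27.2% |

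Check by hand at 40 per arm: adjustment multiplies the residual SD by √(1−r²), and the three extra covariates cost a factor of about 1.014. At r = 0.5, 0.866 × 1.014 = 0.878, or −12.2%. At r = 0.3, 0.954 × 1.014 = 0.967, or −3.3%.

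The ratio factor at 40 per arm becomes 1.49, 1.43 and 1.34 for r = 0.3, 0.5 and 0.7. At 30 per arm it becomes 1.59, 1.52 and 1.41. Without balance within site, the cost at r = 0 is +2.1% (40 per arm) or +2.8% (30 per arm). Break-even r is about 0.15–0.2.

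**3. If site or season matters**

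At 40 per arm and r = 0.3, a site difference of 0.1 or 0.2 log10 (assumed) raises the narrowing from 3.3% to 4.1% or 6.3%. A season difference of the same size gives 4.0% or 6.2%.

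**4. Missing Day 1 titres**

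With 5% missing, 0.05 × 80 = 4 women. At r = 0.3 and 40 per arm, a complete-case model narrows the interval by 0.5%. Filling in the overall mean log titre, ignoring arm, narrows it by 3.0%.

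**5. Scale**

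Take a GMT 25% lower in one arm, with SD 0.4 and 40 per arm. The SD on the natural log scale is 0.4 × 2.3026 = 0.921. By the delta method, SE of the difference = (0.921/√40) × √(G₁² + G₂²).
- 20 vs 15: SE = 0.1456 × 25 = 3.64; difference −5 (95% CI −12.2 to 2.2).
- 300 vs 225: SE = 0.1456 × 375 = 54.6; difference −75 (−183.7 to 33.7).
- Ratio in both cases: 0.75 (0.75/1.51 to 0.75 × 1.51, i.e. 0.50 to 1.13).

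**The case against.** The best reply is that this is a descriptive pilot and the plan is coherent as it stands. The unadjusted comparison is unbiased, its interval is valid, and no decision turns on a narrower one. All of that stands.

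The word difference is plausibly a slip. The same sentence form is used throughout Section 7 for proportions, GMTs are means of logs, and a log-scale difference back-transforms to a ratio. The ratio could also be rebuilt from the arm GMTs and their intervals. So the scale point alone is a minor text correction, though two analysts could still implement the present wording differently.

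On adjustment, the covariate list is open and the gain depends on an r that the documents do not give. Low r is more likely for delivery and cord samples, and Section 1.1 stresses titre at delivery. Little gain should be expected there. This limits the size of the benefit, but the cost of adjusting when r is near zero is only a slightly wider interval.

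A log-titre model also needs a rule for influenza titres below the 1:10 starting dilution (Section 6.3). That is true, but the GMTs already planned need the same rule.

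Finally, naming the sample compared may look like a separate matter. It belongs with the model because at Visit 4 the sequential arm is bled before Tdap, and its post-Tdap sample is Visit 7, taken in that arm only (Section 5.1). Comparing pertussis by visit number would set post-Tdap titres against pre-Tdap titres.

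**Conclusion.** The concern holds on both counts, as a worthwhile improvement and not as an error that invalidates the analysis. The maternal and cord pertussis contrast lacks a scale and, read literally, does not match the influenza and infant contrasts. No maternal or cord GMT comparison commits to the Day 1 titre or to site.

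The cost is precision and clarity, not bias. Adjustment makes the interval at most about 2–3% wider if the covariates predict nothing. It makes the interval about 3% narrower at r = 0.3, 12% at 0.5 and 27–28% at 0.7. The percentage changes rest on the assumed r, equal sites and an even season split. The ×/÷ factors also rest on the assumed SD of 0.4. Confidence in a material gain is moderate for the post-vaccination samples and lower for delivery and cord.

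**What to change.** 1. In 7.1.3.1, replace the difference with a ratio of GMTs, back-transformed from log titres.
2. For the maternal and cord pertussis and the influenza GMT ratios, replace the optional regression with one pre-specified linear model on log titre: arm, maternal Day 1 log titre (not Visit 4) and site. Add season where both seasons contribute, which excludes Fim2/3 because it is assayed only for 2016–17 (Section 6.1).
3. Name the outcome sample. Maternal post-Tdap pertussis: Visit 4 in the simultaneous arm, Visit 7 in the sequential arm. Maternal post-IIV influenza: Visit 4 in both arms. Delivery and cord: Visit 8.
4. Keep women with a missing Day 1 titre by imputing the overall mean log titre, ignoring arm.
5. Report the unadjusted ratio alongside. Replace the normality condition with a robust or bootstrap interval as a sensitivity check.
6. Leave the exploratory infant subset unadjusted. With about 10 per arm its interval is roughly ×/÷ 2.38 (2.101 × 0.4 × √(2/10) = 0.376; 10^0.376 = 2.38), too few for extra covariates.

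The cost is a word in 7.1.3.1, a short model specification and a few lines of code per comparison. No new visits, samples or assays are needed. The downside is an interval up to about 2–3% wider if the covariates turn out not to predict the outcome.

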### 6.2 Tetanus and Diphtheria Laboratory Analysis

Quantification of antibodies against diphtheria and tetanus toxoids will be performed by ELISA using kits containing an internal standard (AbCam, Cambridge, MA) per the manufacturer's directions. Briefly, wells pre-coated with diphtheria or tetanus antigen are incubated with dilution media as a blank, control specimens that contain a defined amount of anti-diphtheria or anti-tetanus antibody, or an unknown test sample. All specimens are run in duplicate. Primary antibody is allowed to bind for 1 hour at 37°C, plates washed, and secondary antibody allowed to bind for 30 min at room temperature.

Plates are washed again and substrate added; this is incubated for 15 min at room temperature in the dark, followed by reading on a microtiter plate reader at 450 nm. The values from replicate wells are averaged, the background of blank wells subtracted from all other wells, and a dilution curve created using the known controls. Optical density readings are then compared to the standard curve and an absolute value for binding antibodies in international units is calculated. For specimens that have optical density readings higher than the standard curve range, a dilution of the serum/plasma sample is assessed in a repeat assay.

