### **6.3 Influenza Laboratory Analysis**

We intend to utilize the 2016-2017 and 2017-2018 quadrivalent Fluzone (Sanofi) as the IIV study product. As such, reference wild-type, reassortant, or vaccine virus strains representative of the specific viral antigens included in the 2016-2017 and 2017-2018 influenza vaccines will be used to evaluate the relative levels of all four influenza strain-specific antibodies in maternal serum pre- and post-vaccination (60 subjects, 240 samples total). To accomplish these activities all patient samples will be interrogated for influenza antibodies against the strains of interest using the influenza hemagglutination inhibition assay (HI). This assay is considered the “gold-standard” measure by which to evaluate seroconversion/seroprotection in response to seasonal influenza vaccination. This assay will be performed in accordance with the RBL Virology Unit’s fully optimized and approved SOP (RVUSOP004 Influenza HI of Serum Samples). Briefly, test samples will be assayed by HAI as duplicate 2-fold dilution series starting at 1:10. Serum dilutions are then incubated with a concentration of virus verified to possess a known potential for red blood cell (RBC) agglutination. The presence of virus-specific antibodies is visualized via incubation of the virus-serum mixture with a RBC solution; the endpoint titer for a given dilution series is then expressed as the reciprocal of the final dilution in which complete HI is observed. By convention, seronegative samples are defined as having an endpoint HI titer < 1:40 and seropositive samples as having an endpoint titer of ≥ 1:40; and seroconversion as a 4-fold change in endpoint titer relative to pre-immunization baseline or a change from <1:10 to ≥1:40.

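### Tetanus and diphtheria levels are a primary outcome, but the only planned between-arm comparison is the proportion at or above 0.1 IU/mL

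*Combined protocol and SAP*

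**What the plan says.** Section 2.1.1 lists measurement of serum antibody levels as a primary outcome. It names the diphtheria and tetanus toxoids and covers maternal samples before and after vaccination, maternal blood at delivery and cord blood. Section 6.2 describes the toxoid ELISA as quantitative: "an absolute value for binding antibodies in international units is calculated".

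For the toxoids, Section 7.1.3.2 reports the share of women at or above 0.1 "IU/mL post-vaccination for both tetanus and diphtheria ELISAs, in the two treatment groups will be presented along with 95% exact binomial confidence intervals", with an interval for the between-arm difference in that share. It notes that no accepted seroconversion definition exists and adds that "we will evaluate the data to derive a potential post hoc definition for seroconversion".

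The neighbouring sections treat levels differently. For pertussis (7.1.3.1): "A 95% confidence interval of the difference in GMTs between the treatment groups will also be presented". For influenza (7.1.3.3), in addition to seroprotection and seroconversion rates: "A 95% confidence interval of the ratios in GMTs between the treatment groups will also be presented". The exploratory infant pertussis objective (7.1.8) also has a between-arm ratio of geometric means.

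Three general statements touch on levels. Section 7 says that "descriptive statistics and confidence intervals for continuous variables will be presented". The end of 7.1.3 says: "Outcomes listed in Primary Objective 2 may be analyzed using a regression model to adjust for covariates such as BMI or race", as a secondary analysis and only if normality holds. Section 3.2.1 plans a maternal-to-cord ratio as a measure of placental transfer.

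**The concern.** The outcome is a level, the assay measures a level, and the planned contrast discards the level. Tetanus and diphtheria are the only antigens under Primary Objective 2 without a stated between-arm comparison of geometric means, and no reason is given.

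A threshold rate responds to a shift in level only if enough women lie near the threshold. If nearly all are above 0.1 IU/mL in both arms, the two rates agree near 100% even when one arm's levels are half the other's. Whoever then wants to know whether simultaneous vaccination lowers toxoid antibody must choose a comparison after the data are in.

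A smaller, related point concerns seroconversion. Its definition is openly post hoc, but nothing says it will be fixed before results by arm are seen. The study is open label, and Section 5.2.2 blinds only laboratory and pathology staff.

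Section 7 disclaims any power calculation, so the issue is how much the planned interval can tell the reader, not whether a test would meet a criterion.

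**Working it through.** **Is a between-arm comparison of toxoid levels committed to anywhere?**

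- Section 7.1.3.2: proportions only. Seroconversion, if defined, would also be binary.
- Section 7: generic summaries and intervals for continuous variables, with no between-arm contrast, log scale or time point.
- Regression at the end of 7.1.3: optional, secondary and conditional on normality. It refers to the outcomes listed, and the toxoid outcome listed is a proportion.
- Section 3.2.1: a transfer ratio, with no comparison of arms stated.

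None of the four commits to one. The plan states no figure of its own to reproduce.

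**How much could the dichotomy lose?**

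Inputs from the documents: threshold 0.1 IU/mL (7.1.3.2); about 80 women randomised 1:1, so 40 per arm (3.1, 5.2.1). Section 6.3 gives a smaller count, "60 subjects, 240 samples total", for the influenza assays. Nothing applies it to the toxoids, so I use 30 per arm only as a sensitivity case.

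Assumptions, none given in the documents: log-normal levels; SD on the natural-log scale 0.8, 1.0 or 1.2; geometric mean G in one arm and G/2 in the other; Newcombe interval for the difference in proportions.

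Formulas:

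- Proportion at or above threshold = Φ[(ln G − ln 0.1)/SD].
- Chance that the Newcombe interval excludes 0: exact sum over all pairs of binomial counts.
- Ratio of geometric means: SE = SD × √(2/n). The chance that the t interval excludes 1 comes from the noncentral t with 2n − 2 df and noncentrality ln 2/SE.
- 95% CI of the ratio: estimate multiplied or divided by exp(t₀.₉₇₅ × SE).

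Worked case, n = 40, SD = 1.0, G = 1: Φ(ln 10) = 98.9% and Φ(ln 5) = 94.6%, a fall of 4.3 points; the interval excludes 0 in 4% of trials. For the ratio, SE = √(2/40) = 0.224 and noncentrality = 0.693/0.224 = 3.10; the interval excludes 1 in 86.5%.

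Results at 40 per arm, ranges over the three SDs:

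| Higher geometric mean (IU/mL) | Fall in proportion (points) | Difference interval excludes 0 | Ratio interval excludes 1 |
|---|---|---|---|
| 1 to 4 | 0.01 to 6.2 | 0 to 12% | 72 to 97% |
| 0.5 | 10.4 to 13.3 | 34 to 41% | 72 to 97% |
| 0.2 | 21.8 to 30.7 | 53 to 84% | 72 to 97% |

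By SD (0.8, 1.0, 1.2), the ratio figures are 96.9%, 86.5% and 72.3%. They do not depend on G.

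At 30 per arm, the difference interval excludes 0 in 0 to 6%, 20 to 26% and 41 to 72% for the three rows. The ratio interval excludes 1 in 91.0%, 75.2% and 59.5%.

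Width of the ratio interval: the estimate multiplied or divided by 1.43 to 1.71 (40 per arm) or 1.51 to 1.86 (30 per arm).

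Limiting case: if all 40 women in each arm reach 0.1 IU/mL, the Newcombe interval is −8.8 to +8.8 points, whatever the difference in levels.

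**The case against.** The strongest reply has four parts.

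*Partly covered elsewhere.* Section 7 promises summaries of continuous variables, and a normality condition on the regression makes most sense for continuous levels. A route to a level comparison is therefore named in advance. That stands as far as it goes: one should not say that no summary of levels is planned. But a route that is optional and silent on scale and time point is not a commitment.

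*Modest consequence.* The interference concern in Section 1 is about pertussis, which does get a comparison of geometric means. No toxoid margin or decision rule exists, and a recognised protection threshold is a natural reporting scale. This is fair, and nothing planned is biased or invalid. It does not explain why a primary outcome defined as a level has no comparison of levels when influenza has both.

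*Assumed magnitudes.* Geometric means, SDs, the halving and the interval method are all assumptions, and the chance for the planned contrast runs from 0 to 84%. That stands: the documents cannot show whether the loss is near total or small. The direction is stable, since at each SD the ratio is more sensitive in every scenario tried.

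*Extras in the remedy.* Baseline adjustment is not in the main pertussis or influenza analyses, fold rise is not planned for the toxoids, and seroconversion is already labelled post hoc. True; the core repair stands without these additions.

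**Conclusion.** The concern holds. For tetanus and diphtheria, the plan commits to one between-arm contrast, and it is dichotomised, although the primary outcome is the antibody level. How much is lost depends on where the levels lie. Under the stated assumptions, with 40 per arm and a true halving, the planned interval detects almost nothing at geometric means of 1 IU/mL and above, and a ratio interval would do clearly better. Near 0.2 IU/mL the gap narrows but remains. This should be corrected; it does not invalidate the pilot.

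**What to change.** Amend Section 7.1.3.2 as follows.

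1. For each toxoid, report the geometric mean concentration by arm and the between-arm ratio with a 95% CI from the log scale. Do this at the post-Tdap sample (Visit 4 in the simultaneous arm, Visit 7 in the sequential arm), in maternal blood at delivery and in cord blood. Naming the visit matters because the sequential arm's Visit 4 sample precedes Tdap.
2. Use the log Visit 1 level as covariate; that sample precedes vaccination in both arms.
3. Keep the 0.1 IU/mL rate and its interval as supportive.
4. If a fold rise is also reported, state the baseline sample in each arm. With the Visit 4 window at Days 22–29 and the Visit 7 window at Days 43–57, Visit 1 (Day 1) to post-Tdap spans 21 to 28 days in the simultaneous arm and 42 to 56 days in the sequential arm. The sequential arm's immediate pre-Tdap sample is Visit 4.
5. Label any seroconversion cut-off exploratory, and fix it on pooled data without arm labels before results by arm are produced.

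The cost is wording only, since the ELISA values will already exist. The downside is 2 toxoids × 3 sampling points = 6 more descriptive contrasts, to be shown as estimates with intervals and no claim of significance.
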